10.2. Analysis of Secondary Efficacy Endpoints

Secondary efficacy endpoints will be analyzed and reported based on subjects in the ITT population, if not otherwise specified. All secondary efficacy endpoints will be analyzed at the time when the primary endpoint is due for analysis.

10.2.1. Time to Response

Time to response (TTR) is defined as the time from treatment start until a documented disease response (either CR, CRi or PR). Subjects not observed with a response will not be included in the analysis. Summary statistics (n, mean, StdDev, median, Q1, Q3, min, max) will be provided for time to response.

10.2.2. Overall Response Rate

Overall response rate defined as the proportion of subjects with best response (CR, CRi or PR) among all subjects in the ITT population (i.e. subject will be considered as having a response if they achieve at least PR). Subject achieving less than PR (i.e. 'treatment failure') or having no assessment will be considered as a non-responder. If a subject is missing some assessments, their best response from available assessments will be selected as the response. Responses occurring after a treatment failure will not be considered. All assessments collected while a subject is under study treatment (incorporating, wherever applicable, the 28 day rule, i.e. last dose plus 28 days) will be considered.

The ORR formula will be the following

$$\text{ORR} = (\text{number of CR, CRi or PR from start to the end of period under analysis}) / (\text{number of subjects within the ITT population}).$$

The ORR rate at the end of Cycles 1, 2, 3, 4, 8 and 12 will be categorized, and the rate will be calculated for each cycle dividing the number of subjects with response in the cycle by the number of subjects entering the cycle. The formula will be the following

$$\text{ORR cycle}_i = (\text{number of CR, CRi or PR from start of Cycle } i \text{ to the end of Cycle } i) / (\text{number of subjects entering Cycle } i \text{ within the ITT population}).$$

Proportions will be presented as percentages with frequency counts together with the Clopper-Pearson 95% CI, at the end of each pre-specified cycle.

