- ^r BMA/biopsy and peripheral blood smear must be collected at the completion of the 21-day treatment period within 6 days **before dosing for the subsequent cycle** (ie, between Day 22 to Day 27 of that cycle) in Cycles 1, 2, 3 and 4. If morphologic CR/CRi is achieved within the first 2 cycles, the BMA/biopsy and peripheral blood smear will not be required at the end of Cycle 3. These assessments are required for all subjects at the end of Cycle 4, and at the Treatment Discontinuation Visit or at the time of suspected relapse (whichever occurs first). An IWG response assessment will be performed whenever a bone marrow assessment is performed.
- ^s For subjects who are assessed as having partial response, the BMA/biopsy and peripheral blood smear will be repeated at Cycle 8 **unless** the subject goes to allogeneic HSCT, and at the Treatment Discontinuation Visit or at the time of suspected treatment failure (whichever occurs first).
- ^t During the study, repeat of bone marrow local cytogenetic/FISH testing is to be completed whenever a bone marrow aspirate/biopsy is obtained. However, if the cytogenetics/FISH results are 'normal' at screening or at any point during the study, no further cytogenetic/FISH analysis is required, except at the Treatment Discontinuation Visit or at the time of relapse (whichever occurs first).
- ^u Bone marrow aspirate/biopsy, peripheral blood smear, cytogenetic testing, and an IWG response assessment will be measured at the Treatment Discontinuation Visit or at the time of suspected relapse (whichever occurs first). If clinically inappropriate per the treating site, the subject may have bone marrow evaluation omitted if peripheral blast results are collected.
- [REDACTED]
- [REDACTED]
- [REDACTED]
- [REDACTED]
- ^z Blood PK sampling time points are specified in Table 3. [REDACTED]

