5.2. Calculation of Treatment Start Dates, Cycles, and Treatment End dates

Treatment will commence on Day 1 and planned cycle lengths are 28 days. Day 1 of treatment is defined as the first day of study drug. Day 1 of a cycle is defined as day 1 of study drug for the given cycle as recorded on the eCRF.

Cycle end dates are defined as the day before Day 1 of the following cycle. The treatment end date, and the end date of the last cycle, will be calculated as follows:

- For subjects who discontinue prior to the clinical cutoff date, treatment end date is the date of treatment discontinuation from the treatment disposition page in the eCRF;
- For subjects who are still on treatment at the time of study closure or clinical cutoff, the last date of planned cycle (27 days after first dose of the last cycle) will be used as the treatment end date.

The cycle number for each date of interest, e.g. Adverse Event (AE) start date, will be calculated based on the cycle window set by their start and end dates.

The following rules will be implemented for cycle calculations for Treatment-Emergent AEs (TEAEs):

- TEAEs present on or after Day 1 Cycle *i* but before Day 1 of the subsequent Cycle belong to Cycle *i*;
- All TEAEs which occur after Day 1 of the last cycle will be included only in the last cycle.

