10.2.3. Disease Assessment Outcome

Disease assessment outcome (DAO) at the end of Cycles 1, 2, 3, 4, 8 and 12 of lenalidomide administration shall be categorized according to the Cheson criteria (Cheson, 2003, see Section 18.1) into the following categories: CR, CRi, PR, Treatment Failure (Resistant Disease, Aplasia, Indeterminate Cause, Relapse after CR or CRi, Molecular or Cytogenetic relapse), Missing/not done. Responses occurring after a treatment failure will not be considered. The DAO rate for each of the response criteria will be calculated as the total number of subjects in a given response category at each time point over the number of subjects entering each corresponding cycle. The formula will be the following:

DAO category cycle_i = (number of subjects with DAO category from start of Cycle i Day 1 to the end of Cycle i) / (number of subjects entering Cycle i within the ITT population)*100.

Proportions will be presented as percentages with frequency counts together with the Clopper-Pearson 95% CI, per response category at the end of each pre-specified cycle.

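### By-cycle overall response rate can understate response at Cycles 3 and 8, because complete responders with no scheduled marrow stay in the denominator

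*SAP*

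**What the plan says.** SAP 10.2.2 defines two quantities. The overall ORR takes each subject's best response over the period, divided by the ITT population. The by-cycle ORR is reported at the end of Cycles 1, 2, 3, 4, 8 and 12, by this rule: "rate will be calculated for each cycle dividing the number of subjects with response in the cycle by the number of subjects entering". Its numerator is limited to CR, CRi or PR between the start and end of Cycle i.

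SAP 10.2.3 builds the disease assessment outcome table the same way, "over the number of subjects entering each corresponding cycle". Its list of categories ends with "Molecular or Cytogenetic relapse), Missing/not done".

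SAP 5.2 closes each window: "Cycle end dates are defined as the day before Day 1 of the following cycle".

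The marrow schedule is in the footnotes to Protocol Table 2:
- Footnote r, on early complete response: "CR/CRi is achieved within the first 2 cycles, the BMA/biopsy and peripheral blood smear will not be required at the end of Cycle 3". A marrow is required for everyone at the end of Cycle 4.
- Footnote r also says: "An IWG response assessment will be performed whenever a bone marrow assessment is performed".
- Footnote s: "For subjects who are assessed as having partial response, the BMA/biopsy and peripheral blood smear will be repeated at Cycle 8".
- Table 2 marks the Cycle 5-12 column, but footnotes r and s name no Cycle 12 marrow except at discontinuation or at suspected relapse or failure.

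**The concern.** The formulas and the schedule were not aligned. CR and CRi require a marrow blast result below 5% (Protocol Appendix D), so a subject with no marrow in the cycle has no documented CR/CRi in it. At Cycles 3 and 8 the subjects excused from a marrow are those already in complete remission. They count as entering the cycle and cannot count as responding in it.

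A fall in by-cycle ORR from Cycle 2 to Cycle 3, or from Cycle 4 to Cycle 8, could then come from the visit schedule and be read as loss of response. Disease assessment outcome is a listed secondary endpoint and is defined only by cycle, so it has no headline figure to correct that impression.

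**Working it through.** **Plan's own figure.** The documents give none for the by-cycle rates. The two-stage design (18 then 25; at least 3 of 18 to continue; at least 8 of 43 for activity; 10% against 25%) reproduces, with exact type I error 0.048 and power 0.800. It does not enter this point.

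**Can a Cycle 2 marrow count in Cycle 3?** No. Scheduled marrows fall on Days 22 to 27 of a cycle, and Cycle 2 ends the day before Cycle 3 Day 1, so the result belongs to Cycle 2. Neither 10.2.2 nor 10.2.3 carries a response forward into a later cycle's rate.

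**Formula.** Let N be the ITT subjects entering the cycle, k those with a response documented in it, and c the ongoing complete responders with no marrow in it.
- Planned rate = k/N.
- Rate if those c subjects were counted as still responding = (k + c)/N.
- Shortfall = c/N, which is zero when c = 0.

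**Size per subject (c = 1).** The documents give no N for any cycle, so these are assumptions:

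| N entering | Shortfall (points) |
|---|---|
| 43 | 1/43 = 2.3 |
| 30 | 1/30 = 3.3 |
| 20 | 1/20 = 5.0 |
| 8 | 1/8 = 12.5 |
| 5 | 1/5 = 20.0 |

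The by-cycle denominator is drawn from the ITT population, which could reach 43 + 4 = 47; then 1/47 = 2.1 points.

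**How it would read if that subject were the only responder (k = 0, c = 1), with Clopper-Pearson 95% intervals.**
- Cycle 3, N = 30: reported 0/30 = 0.0% (0 to 11.6) instead of 1/30 = 3.3% (0.1 to 17.2).
- Cycle 8, N = 8: reported 0/8 = 0.0% (0 to 36.9) instead of 1/8 = 12.5% (0.3 to 52.7).

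The intervals overlap widely.

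**How many subjects?** Possibly very few. SAP section 16 drops the durable response summary in a list explained by low counts (1 or fewer) or redundancy, without saying which reason applies. That is why only c = 1 is shown.

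**Outcome table.** The CR and CRi rows together lose the same c/N. The subjects reappear under Missing/not done, mixed with those who missed a scheduled assessment. The PR and treatment failure rows are not lowered by this route.

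**The case against.** **The shortfall is conditional.** The Cycle 3 marrow is waived, not barred. Protocol 6.20.4 lists IWG assessment at Cycles 1 to 4 without repeating the waiver, and Protocol 6.20.1 provides for marrows to confirm a response suspected from blood counts. A site that takes a marrow puts the subject back in the numerator. This stands: the rate can be understated, but a reader who infers that it must be goes beyond the documents. For Cycle 8, 6.20.4 agrees with footnote s, so only the confirmatory marrows in 6.20.1 remain.

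**The no-assessment rule.** SAP 10.2.2 says that a subject with less than PR "or having no assessment will be considered as a non-responder". A reader might take this as an instruction to score unassessed complete responders as failures in each cycle. It belongs to the overall ORR definition. So does the next sentence, which uses the best available response when some assessments are missing. Neither governs the by-cycle formula; the by-cycle window alone produces the shortfall.

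**The outcome table discloses the gap.** Correct. What remains there is that one row mixes unscheduled with missed assessments.

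**Few subjects are exposed.** Complete responders who go to transplant leave treatment and so do not enter later cycles. This reduces c, especially at Cycle 8, but does not correct the rule.

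**SAP section 16 already changed the denominator.** It replaced subjects completing the cycle with subjects starting it. An ongoing complete responder is in both, so the mismatch is untouched.

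**Conclusion.** The point holds as a minor one. By-cycle ORR at Cycles 3 and 8 can be understated by exactly c/N: 3.3 points per subject if 30 enter, 12.5 if 8 enter, and nothing if every ongoing complete responder has a marrow in the cycle. The denominators are assumed, and c may be 0 or 1. The CR/CRi percentages in the outcome table are lowered equally, but visibly.

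Cycle 12 has a related gap, because the footnotes name no routine marrow there for anyone. A reader might conclude that the Cycle 12 results are meaningless. That goes too far, since the outcome table would show unassessed subjects as Missing/not done.

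A reader might also infer that the trial's conclusion is at risk. It is not. The primary endpoint keeps a CR/CRi seen at any point in Cycles 1 to 4, the overall ORR uses best response, and the two-stage decision rests on the primary endpoint. The by-cycle rates are descriptive.

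**What to change.** 1. At Cycles 3, 8 and 12, in both the by-cycle ORR and outcome tables, show subjects whose last outcome was CR/CRi and who had no scheduled marrow in a separate row, 'not scheduled (last outcome CR/CRi)'. Keep it distinct from Missing/not done, and do not label these subjects non-responders. The documented rate k/N and the sum (k + c)/N then bracket the possible range for this group; in the Cycle 8 example, 0.0% to 12.5%. Do not move them into the CR/CRi rows: the last marrow required of everyone is at Cycle 4, about 4 x 28 = 112 days before the Cycle 8 assessment and 8 x 28 = 224 days before Cycle 12.
2. Keep the protocol-specified by-cycle rate, and beside it present cumulative best response by the end of each listed cycle over the ITT population. This is the existing overall ORR formula cut at each cycle. Note that it does not show loss of response.
3. Declare the change in SAP section 16, and reconcile Protocol 6.20.4 with Table 2 footnote r on the Cycle 3 assessment.

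The cost is SAP wording, programming, one more declared departure from the protocol and a protocol clarification. The remaining weakness is that the true status of the 'not scheduled' subjects at Cycles 8 and 12 stays unknown.

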10.2.3. Disease Assessment Outcome

Disease assessment outcome (DAO) at the end of Cycles 1, 2, 3, 4, 8 and 12 of lenalidomide administration shall be categorized according to the Cheson criteria (Cheson, 2003, see Section 18.1) into the following categories: CR, CRi, PR, Treatment Failure (Resistant Disease, Aplasia, Indeterminate Cause, Relapse after CR or CRi, Molecular or Cytogenetic relapse), Missing/not done. Responses occurring after a treatment failure will not be considered. The DAO rate for each of the response criteria will be calculated as the total number of subjects in a given response category at each time point over the number of subjects entering each corresponding cycle. The formula will be the following:

DAO category cycle_i = (number of subjects with DAO category from start of Cycle i Day 1 to the end of Cycle i) / (number of subjects entering Cycle i within the ITT population)*100.

Proportions will be presented as percentages with frequency counts together with the Clopper-Pearson 95% CI, per response category at the end of each pre-specified cycle.

10.2.4. Durable Response Rate

Durable response rate is defined as the proportion of subjects achieving a bone marrow confirmed CR/CRi, as collected in the Modified IWG Response Assessment page of the eCRF, lasting at least 3 months (from time complete response observed until treatment failure or worse) or until transplantation if earlier among all subjects eligible for durable response rate analysis (all ITT population subjects that achieve at least a CR or CRi, provided the CR/CRi is confirmed in a bone marrow sample).

A durable response is a response, either CR or CRi, maintained for at least three cycles (or 84 days) from the first time a response is observed, either CR or CRi whichever occurs first. Durable response occurs when the responses assessed thereafter the first observed CR/CRi are either CR or CRi until at least 84 days after the first observed CR/CRi. If the subject undergoes a transplant before 84 days, the subject will be considered as having achieved a durable response. A CR or CRi observed after a PR or treatment failure will not be considered. If a subject has a PR or treatment failure directly following a missed assessment(s) then consider only up to the last completed assessment prior to the missed assessment(s). Should only one assessment be missing (i.e. no consecutive missing assessment) and the next available assessment directly following the missing assessment shows the subject to still have either a CR or CRi then the CR or CRi can still be considered. Any completed disease assessment following 2 or more consecutively missed disease assessments will not be considered.

Proportions will be presented as percentages with frequency counts together with the Clopper-Pearson 95% CI.

10.2.5. Transplantation Rate

The proportion of subjects undergoing a HSCT after treatment start during the conduct of this study will be calculated over the total number of subjects in the ITT population. Proportions shall also be calculated based on whether the transplantation is the first, second, or subsequent transplants post PI administration.

Proportions will be presented as percentages with frequency counts together with the corresponding Clopper-Pearson 95% CI. Collected data will be also listed.

10.2.6. Subject/blast Characteristics Correlating with Response

Laboratory results obtained at baseline/screening [peripheral white blood cell (WBC) and blast count, bone marrow blast percentage, cytogenetics, molecular alterations, etc.] will be evaluated in association with response parameters by means of correlation. Response will be categorized in two levels (response and non-response), as done for the primary efficacy endpoint analysis and for ORR analysis.

The following parameters will be analyzed:

- Hematology
 - WBC count
 - Absolute blasts
 - Absolute neutrophils
 - Platelets
- Peripheral blood smear blasts
- Bone Marrow differential
- Cytogenetics (Karyotype Description)
 - t(8;21)
 - inv(16)
 - Normal
 - +8
 - t (9;11)
 - complex (≥ 3 abnormalities)
 - -5
 - -7
 - 5q-
 - 7q-
 - 11q 23 abnormalities
 - inv (3)
 - t (3;3)
 - t (6;9)
 - Other
- Cytogenetics (Gene mutations)
 - FLT3-ITD
 - FLT3-TKD
 - NPM
 - CEBPA
 - MLL
 - WT
 - NRAS
 - None

Point-biserial correlation coefficient will be computed for continuous parameters, while rank point-biserial correlation coefficient will be computed for parameters expressed as ordinal categories (e.g. megakaryocytes and cellularity). Phi coefficient will be computed for parameters expressed as nominal dichotomous categories.

Summary statistics and listings will be provided for cytogenetics.

CELGENE PROPRIETARY INFORMATION

11. SAFETY ANALYSES

The purpose of this section is to describe the safety analyses for the treatment period of the study (after signing ICF/IAF and until the 28-day safety follow-up visit). For subjects who will enter the OEP, AEs will be reported for the two treatment periods, the fixed and the OEP period, the latter including the 28-day safety follow-up visit.

Drug-related SAEs will be collected and reported for the whole period of the study, i.e. including the 5 year follow-up period.

Listing for safety analyses will be provided for safety population if not otherwise specified.

11.1. Adverse Events

Adverse Events will be coded according to MedDRA dictionary version 18.0 or higher. The severity of AEs will be graded according to the National Cancer Institute Common Terminology Criteria for Adverse Events (NCI CTCAE) (version 4.03, May 2009), except for tumor flare reaction, which is defined using CTCAE version 3.

All AEs will be recorded by the Investigator from the time the subject signs the ICF/IAF until 28 days after the last dose of lenalidomide and those SAEs made known to the Investigator at any time thereafter that are suspected of being related to lenalidomide.

In the occurrence of partial dates, refer to Appendix 18.4 where the date imputation guideline is located.

Treatment-emergent adverse events (TEAEs) are defined as any AE occurring or worsening on or after the first treatment of the IP and within 28 days after the last dose administration date. All TEAEs, AEs leading to IP discontinuation, AEs leading to dose reduction/ interruption, AEs related to lenalidomide, and SAEs and AEs leading to death will be summarized by cycle up to a 28-day period after last cycle (see section 5.2), as well as by subject worst recorded grade per event type, SOC, PT and grade. A summary of AEs with NCI CTCAE v 4.0 Grade 3 or higher (except for tumor flare reaction, which is defined using CTCAE version 3), as well as the most frequent PTs, will also be provided by grade and PT. If a subject experiences the same AE more than once with different severity grade, then the event with the highest grade will be tabulated in “by grade” tables. If a subject experiences multiple AEs under the same PT/SOC, then the subject will be counted only once for that PT/SOC. In addition, AEs with a missing intensity will be presented in the summary table as an intensity category of “Missing”.

11.1.1. Overview of TEAEs

The number and percentage of subjects experiencing TEAEs will be summarized in the following categories:

- All TEAE
- All TEAE related to lenalidomide;
- NCI CTC grade 3/4 TEAE;
- Treatment related NCI CTC grade 3/4 TEAE;

- NCI CTC grade 5 TEAE;
- Serious TEAE;
- Treatment-related serious TEAE;
- Serious TEAE leading to dose discontinuation;
- TEAE leading to dose discontinuation;
- TEAE leading to dose reduction;
- TEAE leading to dose interruption;
- TEAE leading to death.

11.1.2. TEAEs by System Organ Class and Preferred Term

The incidence of TEAEs will be summarized by MedDRA SOC and PT. The intensity of AEs will be graded 1 to 5 according to the NCI CTCAE.

Tables summarizing the incidence of TEAEs will be generated for each of the following:

- All TEAEs;
- All TEAEs with CTCAE grades 3 or 4;
- All TEAE by CTCAE grade;
- TEAEs reported as treatment-related;
- Treatment-related CTCAE grade 3 or 4 TEAEs;
- Treatment-related CTCAE grade 3 or 4 TEAEs by CTCAE grade;
- CTCAE grade 5 TEAEs;
- Serious TEAE;
- TEAEs leading to death
- Treatment-related serious TEAEs;
- Serious TEAEs leading to discontinuation of lenalidomide
- TEAEs leading to discontinuation of lenalidomide
- TEAEs leading to dose reduction;
- TEAEs leading to dose interruption;
- TEAEs by cycle;
- TEAEs with CTCAE grade 3 or 4 by cycle;
- Non-treatment emergent AEs.

Frequency distributions for shift from baseline to the maximum CTCAE grade during treatment period will be presented for all grades and focusing on grade 3 or 4.

System organ classes are sorted by descending order of frequency of SOC, and by descending order of frequency of PT within SOC, according to the overall column. In tables where the two treatment periods and the overall period are reported, the sorting order will be defined on the basis of frequencies found in the overall column.

For all tables showing results by cycle, OEP and 12th cycle will be considered as a unique cycle labelled “Cycle 12 and higher”.

Listing of AE, SAE, SAE of special interest and AE leading to treatment discontinuation will be provided in separated displays.

11.1.3. Adverse Events of Special Interest

Selected TEAEs/ serious AEs (SAEs) of interest, including second malignancies and cardiovascular events, as determined by the mechanism of action, known class effects, or TEAEs observed to date will be summarized. Standardized MedDRA queries (SMQs) will be used in the search strategy for some of the selected AEs of special interest related to study drug, intending to aid in case identification. The groupings of selected AEs, described by one phrase or topic term will be determined by clinicians based on SMQ or relevant search terms and provided to statistician, prior to database lock.

Analysis of AEs of special interest will be presented with tabulations for: summary of TEAEs of interest by category, TEAEs of interest, NCI-CTCAE grade 3 or 4 TEAEs of interest, TEAEs of interest related to study medication, NCI-CTCAE grade 3 or 4 TEAEs of interest related to study medication, serious TEAEs of interest, serious TEAEs of interest related to study medication, serious TEAEs of interest and TEAEs of interest leading to study medication discontinuation, TEAEs of interest by CTCAE maximum grade 1 or 2 and 3 or 4 and TEAEs of interest by CTCAE maximum grade. The following AE of interest categories and preferred terms include but are not limited to:

- Thrombocytopenia and bleeding
- Neutropenia and infection
- Venous thromboembolism
- Cutaneous reactions
- Hypersensitivity and angioedema
- Diarrhoea and constipation
- Peripheral neuropathy
- Cardiac failure and cardiac arrhythmia
- Renal failure
- Ischaemic heart disease (previously myocardial infarction)
- Interstitial lung disease (interstitial pneumonitis)
- Liver function laboratory abnormalities
- Second primary malignancies (SPMs)

- Tumor lysis syndrome (TLS)
- Tumor flare reaction (TFR)
- Graft versus host disease (GVHD)

Frequency distributions for shift from baseline to the maximum CTCAE grade during treatment period will be presented for all grades and focusing on grade 3 or 4.

All AEs of special Interest will be identified by appropriate MedDRA preferred term.

